5.4 Subjects Withdrawal Criteria

During the study, the subject may withdrawal due to the following reasons.

5.4.1 Investigator's Decision

1. The investigator considers it necessary to stop the trial due to medical ethics;
2. Unacceptable adverse event (AE) occurred and the investigator judged that it was not appropriate for the best interest of the subjects to continue the study treatment;
3. Subjects significantly violate the study protocol, and the investigator determines that the study treatment needs to be terminated;
4. Disease progression is confirmed according to efficacy evaluation criteria (unless the investigator determines that the subject would clinically benefit from continued treatment);
5. Prior to the last biological samples, subjects use other medications that might influence the evaluation of the study drug;
6. Other conditions that the investigator determines requiring withdrawal from the study treatment.

5.4.2 Subjects Withdrawing on Their Own

Subjects who are not willing to continue the study have the right to withdraw from the study at any time. If subjects do not explicitly request to withdraw the study, but they are no long receive doses or assessments, these subjects are also considered to have “withdrawn” or “dropped out”.

The primary reasons for discontinuation of treatment of a subject with the study drug will be clearly documented in the subject's medical record and recorded on the appropriate case report form (CRF). Once a treatment is permanently discontinued, the subject will not be allowed to be retreated. In the case of subjects lost to follow-up, the last-know-alive date as determined by the investigator should be reported and documented in the subject's medical records.

If a subject discontinues study drug temporarily, for example, as a result of an AE or serious adverse event (SAE), every attempt should be made to perform the required study-related follow-up and procedures. If this is not possible or acceptable to the subject or investigator, the subject may be withdrawn from the study and the circumstances clearly noted in the source documents. The reasons for withdrawal or lost to follow-up must be documented in the CRF. All data should be collected up until the point of withdrawal included in the study. This data will be documented on CRF and included in the analysis of the study.

5.5 Criteria for Trial Termination

5.5.1 Serious Safety Concerns

1. the dose stopping criteria (see 4.4 Dose Escalation/Stopping Criteria) has been reached, in the judgement of the investigator, the trial should be stopped;
2. During the trial, a significant mistake of the trial protocol is identified, which makes it difficult to evaluate the effect of study drug, or cause significant safety concerns;
3. A significant deviation of study protocol occurs, and the investigator decide that it is difficult to evaluate the study drug with further continuation.

5.5.2 Investigator's Request

During the trial, there may be some circumstances that the investigator cannot continue a trial. It is required that the investigator must notify subjects, sponsors, and IRB or the early termination and state reasons.

5.5.3 Sponsor's Request

Sponsor may request to early terminate the trial due to following reasons:

- Financial difficulties;
- Management;
- Investigator cannot obey the protocol, and all other required laws and rules;
- The study site cannot enrol enough subjects;
- Other concerns.

If deciding to early terminate the trial, the sponsor must notify the investigator, and IRB in writing with reasons, prior to the early termination.

5.5.4 IRB and/or FDA's Request

IRB and FDA has the right to early terminate the trial.

6 Description of Study Treatment

6.1 Study Treatment

FWD1802 is an oral solid dosage form manufactured in strengths of 5mg, 25mg and 150 mg, containing the following inactive ingredients: mannitol 160C, microcrystalline cellulose PH-101, hydroxypropyl methylcellulose (LV) E5 LV, sodium starch glycolate DST, magnesium stearate LIGAMED MF-2-V-MB, silicon dioxide SYLOID 244 FP, Film Coating System Opadry®321A620006-CN Yellow, and purified water.

6.2 Administration

FWD1802 will be orally administered under fed conditions. The dose will depend on the cohort the subject is assigned to.

6.3 Study Drug Packaging and Labeling

FWD1802 tablets are packaged in the HDPE (high density polyethylene) bottles for oral solid dosage form and sealed with polypropylene (PP)/low density polyethylene (LDPE) child-resistant caps (CRC) including desiccant . 5 mg tablets are available in 30 mL HDPE bottles/CRC of 30 film coated tablets, 25 mg and 150 mg tablets are available in 60 mL HDPE bottles/ CRC of 35 film coated tablets. The contents of the label will be in accordance with all applicable regulatory requirements. An example of a study drug label for FWD1802 is shown in

IND Study No.: XX	Protocol Number: FWD1802-001	
FWD1802 Tablet 5 mg, 25 mg, 150 mg For oral use, Administer as per protocol		
Lot No.: XXXX	Expiry Date: XXXX	Subject Number: XXXX
Dosage Units: XX tablets per bottle	Storage condition: Stored at $\leq 25^{\circ}\text{C}$, sealed and dried, protected from light.	
For Clinical Trial Use Only		
Study Sponsor: Shenzhen Forward Pharmaceuticals Co., Ltd.		
Caution: New drug limited by United States law to investigational use		

Figure 2.

IND Study No.: XX	Protocol Number: FWD1802-001	
FWD1802 Tablet 5 mg, 25 mg, 150 mg For oral use, Administer as per protocol		
Lot No.: XXXX	Expiry Date: XXXX	Subject Number: XXXX

Dosage Units: XX tablets per bottle	Storage condition: Stored at $\leq 25^{\circ}\text{C}$, sealed and dried, protected from light.
For Clinical Trial Use Only	
Study Sponsor: Shenzhen Forward Pharmaceuticals Co., Ltd.	
Caution: New drug limited by United States law to investigational use	

Figure 2. An example of FWD1802 label

6.4 Study Drug Storage

The study drug should be stored in sealed and dry containers, 2~8°C, keep out of light, as per the requirements on the label.

Study drugs must be dispensed or administered according to procedures described herein. Only subjects enrolled in the study may receive the study drugs. Only authorized site staff may supply or administer the study drugs. All study drugs must be stored in a secure area with access limited to the investigator and authorized site staff. Investigational sites should use appropriate labeling, which addresses storage conditions and expiration post dispensing, per institutional and regulatory guidelines. Shenzhen Forward Pharmaceuticals Co. Lt will assure that the stability of the study drug is monitored to ensure suitability for continued use at the investigational site.

The details information of study drug please refer to [3.2 P Drug Product](#).

6.5 Study Drug Accountability

The investigator is responsible for ensuring adequate accountability of all used and unused study drug. This includes acknowledgment of receipt of each shipment of study drug (quantity and condition) and maintaining dispensing records. Any study drug that is not used must be recorded in the source and/or dispensing records. Missed doses should be clearly documented along with the reason. All study drug supplies and associated documentation will be reviewed and verified by the study monitor. Study drug should be retained by the site; the site will follow the pharmacy instructions on disposal and/or destruction of all unused supplies. Copies of all forms, and documentation regarding drug receipt and drug accountability records, will be retained according to the regulations governing record retention.

6.6 Study Drug Handling and Disposal

When preparing FWD1802 appropriate precautions for handling chemicals should be taken by the investigational staff, according to institutional policy, although no special precautions need to be taken. After completion of the study, all unused FWD1802 will be inventoried and packaged for shipment by the site to a designated destruction facility or

will be destroyed locally at the investigational site. The study monitor will instruct the site in the disposal and/or destruction of all unused FWD1802 supplies.

6.7 Concomitant Medications

Concomitant Medications means any drug other than the study drug used during the study period (including the screening period and all study visits).

If the use of the combination medications is due to an adverse event, it must be documented and reported in accordance with the relevant regulations and the adverse events and serious adverse events requirements of Section 9 of this protocol.

The supervisor must be notified if the use of the combination medications affects the subject's participation in the study.

Details of all drug combinations must be recorded, including drug name, reason for use, start date, end date or continuation date, indication, and dosage.

The use of other antitumor treatments or experimental drugs is prohibited during the study period. Palliative radiotherapy and bisphosphonate therapy for bone lesions are permitted. Herbal preparations or related over-the-counter preparations containing herbal ingredients are prohibited during the study and treatment period (For details please see Appendix 5).

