11. Subjects with known active hepatitis B virus (HBV) or hepatitis C virus (HCV) infection with abnormal liver function (Absence of infection was defined as HBsAg negative, HBV DNA negative and HCV antibody negative), except to:
 - Subjects who test positive for HBsAg or HBsAb during the screening period may be enrolled if the PCR test result for HCV-RNA is < 500 IU/ml (2000 copies/mL), but receive antiviral treatment according to the investigator's assessment and undergo PCR for HBV-DNA during the study treatment period;
 - Subject has a positive test for HCV antibody at screening and can be enrolled if the PCR test result for HCV-RNA is negative.
12. History of clinically significant cardiovascular disease, such as:
 - Symptomatic congestive heart failure according to New York Heart Association Grades (NYHA $>$ Grade 2);
 - Severe/unstable angina, new angina within last 3 months;
 - Myocardial ischemia and long-term use of drugs for control; according to NYHA, grade III-IV cardiac insufficiency;
 - Any event of acute myocardial infarction within 6 months before screening;
 - Any grade ≥ 2 supraventricular arrhythmia or ventricular arrhythmia requiring treatment or intervention;
 - Any grade atrial fibrillation, coronary/peripheral artery bypass graft, or cerebrovascular symptoms including transient ischemic attack;
 - QTcF (Fridericia's correction formula used) > 470 ms;
 - ECG < 50 bpm.
13. History of serious allergic reactions to the study drugs or excipients used in the protocol.
14. Women who are pregnant or lactating.
15. Prior use of an oral selective estrogen receptor degrader (SERD).
16. Subjects who use drugs or herbal supplements known to be moderate/strong inhibitors of CYP3A2 weeks prior to the first study drug treatment. Subjects who use drugs or herbal supplements known to be moderate/strong inducers of CYP3A4 weeks prior to the first study drug treatment.
17. Received medications which inhibits the production of stomach acid within 2 weeks or 5 drug half-lives (whichever is longer) prior to the first dose of study drugs.

18. Received medications which inhibits P-gp within 2 weeks or 5 drug half-lives (whichever is longer) prior to the first dose of study drugs.
19. Patients with active or chronic corneal disease, other active eye disease requiring ongoing treatment, or any clinically significant corneal disease for which drug-induced keratopathy cannot be adequately monitored.

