8.2 Meals and Dietary Restrictions

FWD1802 (and palbociclib) is administered after meal (within 30 minutes) with approximately 240 ml water. The subjects should start the recommended meal 30 minutes before administration of the drug product. Other dietary restrictions are as follows:

- During each dosing session, subjects will abstain from ingesting caffeine or xanthine containing products (e.g., coffee, tea, cola drinks, and chocolate) for 24 hours prior to the start of dosing until collection of the final PK samples during each session.
- During each dosing session, subjects will abstain from alcohol for 24 hours prior to the start of dosing and during each session.
- Use of tobacco products is not allowed 3 months prior to the screening visit.
- Use of traditional Chinese medicines or herbal products is not allowed 2 weeks prior to and during the study.

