 2. Establish intravenous infusion channels, open respiratory channels, and give endotracheal intubation, cardiac massage and ventilator assisted breathing support when necessary;
 3. Adequate fluid replacement to maintain circulating blood volume: intravenous injection of normal saline or glucose sodium chloride, according to the condition of colloid supplement to ensure circulation osmotic pressure;
 4. Strengthen the heart, improve the pressure, maintain the stability of blood pressure, and ensure the blood supply of important organs: 20-60mg adrenal corticosteroid plus 5% glucose 50-250ml intravenous infusion can be given first, and dopamine can be pumped for maintenance after the blood pressure is stabilized;
 5. Diuretic, diuretic drugs such as furosemide were given according to the volume of urine, sodium bicarbonate was given in appropriate amount, and the urine was alkalinized;
 6. Maintain the balance of water, electrolyte, acid and base;
 7. Anti-arrhythmia;
 8. Symptomatic treatment to maintain nitrogen balance.

- **Anti-allergy treatment**

1. Promethamine 10 mg or promethazine 25-50mg, supine, oxygen inhalation, ensure the airway patently;
2. 0.1% epinephrine 0.1-0.2ml plus 5% glucose by intravenous drip;
3. Use glucocorticoids such as dexamethasone;

- **Correct respiratory and circulatory failure**

Give oxygen or artificial respiration, with kelamine 0.375 g, lobelin 3~6mg injection alternately, every 15~30 minutes. If necessary, intravenous injection 1~2 times strong heart glycoside drug digitalis preparation.

Appendix 5

CYP3A and P-gp Inducers and Inhibitors

	Strong Inhibitors	Strong Inducers
CYP3A4	cobicistat, danoprevir and ritonavir, elvitegravir and ritonavir, grapefruit juice, indinavir and ritonavir, itraconazole, ketoconazole, lopinavir and ritonavir, paritaprevir and ritonavir and ombitasvir (and/or dasabuvir), posaconazole, ritonavir, saquinavir and ritonavir, tipranavir and ritonavir, telithromycin, troleandomycin, voriconazole, ceritinib, clarithromycin, idelalisib, nefazodone, nelfinavir	apalutamide, carbamazepine, enzalutamide, ivosidenib, lumacaftor, mitotane, phenytoin, rifampin
	Moderate Inhibitors	Moderate Inducers

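### Exclusions 16-18 wash out CYP3A, P-gp and acid-suppressing drugs before dose 1, but no on-treatment rule names them, and Appendix 5 is cited only from the herbal ban

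*Protocol*

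**What the plan says.** **Before the first dose (5.3, repeated in the synopsis).** Exclusion 16 covers CYP3A inhibitors, "Subjects who use drugs or herbal supplements known to be moderate/strong inhibitors of CYP3A2 weeks prior to the first study drug treatment", and has a parallel sentence for inducers. The printed text runs the enzyme name and the interval together, but on any reading the period ends at the first dose. Exclusion 17 reads "Received medications which inhibits the production of stomach acid within 2 weeks or 5 drug half-lives (whichever is longer) prior to the first dose". Exclusion 18 reads "Received medications which inhibits P-gp within 2 weeks or 5 drug half-lives", again counted back from the first dose.

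**On treatment.** Section 6.7 has two prohibitions. The first is "The use of other antitumor treatments or experimental drugs is prohibited during the study period". The second is the herbal one: "Herbal preparations or related over-the-counter preparations containing herbal ingredients are prohibited during the study and treatment period (For details please see Appendix 5". It also has a notification rule: "The supervisor must be notified if the use of the combination medications affects" the subject's participation. Section 8.2 adds "Use of traditional Chinese medicines or herbal products is not allowed 2 weeks prior to and during the study", along with limits on caffeine or xanthine products, alcohol and tobacco.

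**Appendix 5** is titled "CYP3A and P-gp Inducers and Inhibitors". It has a CYP3A4 and P-gp table followed by a table of proton pump inhibitors (PPIs).

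**Withdrawal.** Section 4.3 continues dosing until a criterion in 5.4 is met. Item 5 of 5.4.1 is use, before the last biological sample, of another medicine that could affect evaluation of the study drug.

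**The concern.** An eligibility criterion does not bind after enrolment. A site that looks in 6.7 to see whether a patient in Cycle 1 may start a moderate CYP3A inhibitor finds no sentence about that class. A site that follows the only pointer to Appendix 5, looking for details on herbal products, finds a list of something else.

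This matters because of the pharmacology in 1.2.2, which names CYP3A as the main enzyme forming FWD1802 metabolites and the drug as a probable P-gp substrate. In a first-in-human escalation, an inhibitor taken in the DLT window could raise exposure and produce a DLT that the dose alone would not. An inducer could lower exposure and hide one. Cohorts hold 1 to 6 patients, level 1 may hold one, and the next step is a 200% increase to 75 mg, so one altered outcome can change an escalation decision. By-dose PK summaries (10.5.4) and the pooled data used to select the RP2D (4.5) would carry the same distortion.

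**Working it through.** The plan gives no figure to reproduce. The check sets the texts side by side.

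**Step 1. Is each class restricted by name before and during treatment?**

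| Class | Before dose 1 | Named on treatment in 6.7 or 8.2? |
|---|---|---|
| Moderate/strong CYP3A inhibitors and inducers | Exclusion 16 | No (only its herbal supplements are caught, by the herbal bans) |
| Acid suppressants | Exclusion 17 | No |
| P-gp inhibitors | Exclusion 18 | No |
| Antitumour or experimental drugs | Exclusion 2 | Yes, 6.7 |
| Herbal products | Exclusions 2 and 16 (certain herbal products), 8.2 | Yes, 6.7 and 8.2 |

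All three of exclusions 16-18 stop at the first dose. The protocol does extend a rule into treatment where it wants to, as the herbal sentence in 8.2 shows.

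**Step 2. Does Appendix 5 fit the sentence that cites it?** Entries by block: strong CYP3A4 inhibitors 21, strong inducers 8, moderate inhibitors 15, moderate inducers 10, P-gp inhibitors 14, PPIs 5.

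21 + 8 + 15 + 10 + 14 + 5 = 73 entries.

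Eleven names occur twice (for example clarithromycin, verapamil and grapefruit juice), so 73 − 11 = 62 distinct entries. None is a herbal preparation. Outside the contents list the appendix is cited once, from the herbal sentence; exclusions 16-18 do not cite it. Grapefruit juice is listed as both a strong and a moderate CYP3A4 inhibitor but is absent from the dietary rules in 8.2.

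**Step 3. What else could reach these drugs on treatment?** Section 4.3 read with 5.4.1, item 5, makes use of an interfering medicine a ground for ending dosing. PK sampling runs to Cycle 1 Day 15/16 and into Cycles 2 and 3 onward in Parts A and B (7.5.1), so the provision covers the DLT window. However, it sits under the investigator's decisions, names no drug, does not cite Appendix 5, and takes effect only after the medicine has been taken.

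**Step 4. Exposed period.** Part A: 6-day single-dose period + 28-day Cycle 1 = 34 days. Part B: Cycle 1 = 28 days. Later cycles also contribute PK and safety data.

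**The case against.** The strongest reply is that the protocol is not silent. Dosing ends once a 5.4 criterion is met, and a CYP3A or P-gp modulator fits item 5 of 5.4.1. That stands, and it rules out an inference a reader might draw, namely that nothing restricts these drugs on treatment. What is missing is a rule that names them in advance.

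A reader might also size the gap by the list. By a reviewer's classification, 13 of the 62 distinct entries are antitumour drugs already banned by 6.7, and 62 − 13 = 49 are not. That is a count of names, not of likely exposure. Several entries are HIV or HCV antivirals or antiarrhythmics, whose users are largely screened out by exclusions 9, 11 and 12. Five are PPIs, and the protocol reports no pH effect on FWD1802.

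The pharmacology also has limits. Section 1.2.2 reports mainly unchanged drug in liver microsomes, and glucuronidation and N-dealkylation as the main routes in hepatocytes. CYP3A's share of human clearance is not stated. Use of a listed drug as supportive care is an inference: Table 9 asks for supportive therapy and 4.6 refers to optimal management of nausea and vomiting, but neither names a drug, although Appendix 5 lists aprepitant, ciprofloxacin and fluconazole.

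Other safeguards help in part. Concomitant drugs are recorded in detail, the SMC decides each escalation, and 4.5 requires six patients to establish the MTD. None of these tells a site beforehand not to start a listed drug, and the six-patient rule does not protect a next cohort already opened.

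Finally, the misplaced citation may be a drafting slip, with an on-treatment ban intended. That is plausible, but the ban is not written.

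**Conclusion.** The point holds as a missing named on-treatment rule with a misplaced cross-reference. Three drug classes that the sponsor thought worth washing out are not named in any on-treatment restriction, and the list identifying the drugs hangs on a sentence it does not fit. The generic withdrawal provision softens the gap without closing it, because it relies on the investigator's judgement after exposure.

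The consequence is a possible change in exposure, DLT status and by-dose PK in cohorts of 1 to 6, over 34 days in Part A, 28 in Part B, and later cycles. It would be tempting to go further and claim biased DLT rates or a wrong MTD. The protocol does not support that, since it gives no interaction size, frequency of use or CYP3A share of human clearance. No size is claimed. The weight rests on CYP3A and P-gp; acid suppressants are included only for consistency with exclusion 17. It should be fixed because the gap lies in the first-in-human DLT window and the repair is cheap.

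**What to change.** - **6.7:** prohibit moderate and strong CYP3A inhibitors and inducers (including grapefruit juice) and P-gp inhibitors, as listed in Appendix 5, from wash-out to the end of study treatment unless medically necessary. Treat acid suppressants the same way, to match exclusion 17. Appendix 5 lists only PPIs, so either name the other acid-suppressing classes or limit the rule to PPIs.
- **Cross-references:** cite Appendix 5 from that new sentence and from exclusions 16-18, and remove it from the herbal sentence.
- **8.2:** add grapefruit juice to the dietary restrictions.
- **Escalation review:** have any use of a listed drug in the DLT window shown to the SMC at the review it already holds.

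Rules on DLT evaluability or replacement of such patients would be new design choices; they are optional and left to the sponsor.

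The cost is a few sentences in one amendment. The list exists and concomitant medication is already recorded. The downside is an occasional need for an alternative medicine.

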6.8 Assessment of Compliance

When subjects are dosed at the study site, they will receive study drugs directly from the investigator or designee, under medical supervision. The date and time of each dose administered in the clinic will be recorded in the source documents. The dose of study drug will be confirmed prior to dosing by a member of study site staff other than the person administering the study drug. Study site personnel will examine each subject's mouth to ensure that the study drug was swallowed.

7 Study Procedures

The study procedures to be conducted for each subject enrolled in the study are described in the text that follows and presented in Table 1, Table 2 and Table 3. The investigator must document any deviation from protocol procedures and notify the sponsor or contract research organization.

